8.2. Secondary Efficacy Analysis

The secondary efficacy endpoints for Cohort 2 include the following:

AD-ST-33.04 Effective date: 30-Jun-2017

1. Difference in mean percent change from baseline at weeks 1, 2, and 3 in TPSS x TPA between each dose concentration level of ARQ-151 cream and vehicle control.
2. Difference in mean percent change from baseline at weeks 1, 2, 3, and 4 in TPSS between each dose concentration level of ARQ-151 cream and vehicle control.
3. Difference in mean percent change from baseline at weeks 1, 2, 3, and 4 in TPA between each dose concentration level of ARQ-151 cream and vehicle control.

Each of the secondary efficacy endpoints will be analyzed using MMRM methods similar to the primary endpoint; however, no adjustments for multiplicity will occur, and all analyses will be conducted at the $\alpha = 0.05$ level.

Additionally, descriptive statistics for absolute and percent change from baseline to each week (ie, Weeks 1, 2, 3, and 4) will be presented by treatment group.

9. Safety and Tolerability Analysis

Safety will be evaluated from reported AEs, application site reaction assessments, physical examinations, and changes in clinical laboratory values, vital signs, and 12-lead ECGs.

Descriptive statistics will be calculated for quantitative safety data and frequency counts will be compiled for classification of qualitative safety data. No formal inferential statistics will be performed on safety assessments. Individual subject listings will be prepared for all safety data.

All safety analyses will be performed on the Safety Population for each cohort. All safety data will be presented in the listings.

9.1. Adverse Events

An event that is temporally associated with administration of study product is defined as a treatment emergent adverse event (TEAE). Events meeting this definition will be those with a start date during or after administration of the first dose of study drug through the telephone follow-up in each cohort. For AEs occurring on the date of the first dose of study drug, if the time of onset is missing, the AE will be assumed to be treatment emergent.

The causal relationship of the AE to the study drug is determined by the investigator as Unrelated, Unlikely Related, Possibly Related, Probably Related, and Likely Related. These can be mapped to Unrelated (*Unrelated* and *Unlikely Related*) and Related (*Possibly Related*, *Probably Related*, and *Likely Related*).

Adverse event severity grades are reported on a 5-point scale of Grade 1 (*Mild*), Grade 2 (*Moderate*), Grade 3 (*Severe*), Grade 4 (*Life-threatening consequences*), or Grade 5 (*Death related to AE*).

An AE summary table will be presented for the following:

AD-ST-33.04 Effective date: 30-Jun-2017

- All TEAEs
- TEAEs by maximum severity
- Treatment-related TEAE
- TEAEs leading to discontinuation of study drug
- Serious AEs (SAEs)
- Deaths

Summaries of incidence rates (frequencies and percentages) of individual TEAEs by MedDRA (v20.1) system organ class (SOC) and preferred term (PT). Such summaries will be displayed for all TEAEs, TEAEs by maximum severity, and treatment-related. Analysis of TEAEs will be performed by treatment within cohort.

Each subject will be counted only once within each summation level (SOC and preferred term). If a subject experiences more than 1 TEAE within each summation level only, the TEAE with the strongest relationship or the maximum severity, as appropriate, will be included in the summaries of relationship and severity.

Incidence will be presented by descending frequency of SOC and PT within SOC, and then alphabetically within PT where the incidence is the same; this is based on overall subjects.

Missing and partially missing AE start and/or stop dates will be imputed, for the purpose of statistical analysis, according to the specifications described in [Section 6.1.8](#).

In the AE data listings, all AEs will be displayed. AEs that are treatment emergent will be flagged.

9.1.1. Adverse Events Leading to Discontinuation

A summary of incidence rates (frequencies and percentages) of TEAEs leading to discontinuation of study drug, by treatment within cohort, SOC, and PT will be prepared for subjects in the Safety Population for each cohort. No inferential statistical tests will be performed.

A data listing of AEs leading to discontinuation of study drug will also be provided, displaying details of the event(s) captured on the CRF.

9.1.2. Deaths and Serious Adverse Events

Serious AEs will be listed and also tabulated by SOC and PT and presented by treatment within cohort.

Any deaths that occur during the study will be listed.

9.1.3. Other Significant Adverse Events

Not applicable.

9.2. Application Site Reaction Assessments

Application site reaction assessments will be performed on Days 1 and 2 for Cohort 1 and Baseline (Visit 2), Visit 3, Visit 4, Visit 5, and Visit 6 for Cohort 2.

Dermal response reactions are graded using a scale of 0 (*no evidence of irritation*) to 7 (*strong reaction spreading beyond application site*). Additionally, other effects on an A (*slight glazed appearance*) to F scale (*small petechial erosions and/or scabs*) will be noted (where G = *no other effects may be recorded*). Reactions at the site of product application, which may occur post-baseline, should be differentiated from the preexisting inflammation associated with the subject's psoriasis. Changes in dermal response scores, consistent with disease fluctuation, will only be recorded as an AE if the Investigator considers the change to be worse than normal fluctuation.

The numeric application site reaction scores will be summarized individually by using number and percentage of subjects by visit and treatment within cohort.

The numeric application site reaction scores will be summarized by visit and treatment within cohort, in both a continuous manner (using summary statistics) and a categorical manner (using number and percentages). The character other effects scores will be summarized by visit and treatment within cohort using number of percentages.

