8.11.2 Treatment Stopping Rules

Any topically applied product may irritate the skin. If a subject develops an application site reaction with the clinical appearance of an 'irritation reaction', and with a severity of a Dermal Response Score of 5 (erythema, edema and papules) or greater on the scale of Berger and Bowman (8.12.6), treatment should be discontinued for up to one week and may then be resumed if the reaction has, in the opinion of the Investigator, adequately resolved. If the reaction reoccurs, treatment should be discontinued permanently and the subject followed until the reaction resolves.

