8.12.6 Application Site Reaction Assessment (Cohorts 1 and Cohort 2)

Application Site Reaction Assessments will be performed as follows:

Cohort 1: Day 1 and Day 2

Cohort 2: Baseline (Visit 2), Visit 3, Visit 4, Visit 5 and Visit 6

Application site reactions will be graded at the timepoints outlined in the Schedule of Visits and Assessments ([Section 6](#)). Irritation reactions are graded using the scale detailed in the following section ([Berger-1982](#)). Reactions at the site of product application, which may occur post-Baseline, should be differentiated from the preexisting inflammation associated with the subject's psoriasis. Changes in Dermal Response scores, consistent with disease fluctuation, will only be recorded as an AE if the Investigator considers the change to be worse than normal fluctuation.

Dermal Response

- 0 = no evidence of irritation
- 1 = minimal erythema, barely perceptible
- 2 = definite erythema, readily visible; minimal edema or minimal papular response
- 3 = erythema and papules
- 4 = definite edema
- 5 = erythema, edema and papules
- 6 = vesicular eruption
- 7 = strong reaction spreading beyond application site

Other Effects

- A = slight glazed appearance
- B = marked glazing
- C = glazing with peeling and cracking
- D = glazing with fissures
- E = film of dried serous exudates covering all or part of the patch site
- F = small petechial erosions and/or scabs
- G = no other effects

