9.3 Safety Evaluation

The following analyses will be performed; however, no formal inferential statistics will be performed on safety assessments.

Descriptive statistics will be calculated for quantitative safety data and frequency counts will be compiled for classification of qualitative safety data.

Adverse Events:

The assessment of safety will be based mainly on the frequency and percent of subjects who reported treatment-emergent AEs.

Adverse events will be coded using the Medical Dictionary for Drug Regulatory Activities (MedDRA) Version 18.1 or higher. Treatment emergent adverse events (i.e. events with onset dates on or after the start of study drug or with missing onset dates) will be summarized by presenting for each treatment group, the number and percentage of subjects having any AE, having an AE in an individual body system, and having an AE in an individual preferred term. Any other information collected (e.g. severity or relatedness to study medication) will be listed as appropriate.

Application Site Reaction

The numeric application site reaction scores will be summarized individually by using number and percentage of subjects by visit.

Medical History and Physical Examinations:

Medical history for all subjects will be presented in a by-subject listing.

Physical examination findings for all subjects will be presented in a by-subject listing. Changes in physical examinations will be described in the text of the final report.

Clinical Laboratory Results, Electrocardiograms and Vital Signs Measurements:12

All clinical laboratory results, 12-lead ECGs and vital signs measurements and their change from baseline (pre-dose), will be summarized along with time point of collection.

A shift table describing out-of-normal range shifts will be provided for clinical laboratory results.

Prior and Concomitant Medications:

Prior and concomitant medication information for all randomized subjects will be presented in a by-subject listing. Summary tables will be presented by World Health Organization-Anatomical Therapeutic Chemical Classification System (WHO-ATC) therapeutic category and product.

Quick Inventory of Depressive Symptomatology-Self-Report (QIDS-SR):

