4.1. Introduction

Data processing, tabulation of descriptive statistics, calculation of inferential statistics, and graphical representations, except for PK parameter estimation, will be performed primarily using SAS (release 9.4 or higher). All PK parameter estimations will be performed using WinNonlin® version 6.4 or later. If the use of other software is warranted, the final statistical methodology report will detail what software was used for what purposes.

For purposes of this SAP, “treatment within cohort” is defined as enrolled subjects (“Overall”) for Cohort 1 and treatment group (“ARQ-151 0.5%,” “ARQ-151 0.15%,” and “Vehicle”) for Cohort 2. For background and efficacy summaries for Cohort 2, this will be the randomized (ie, planned) treatment group; for safety summaries, this will be the actual (ie, received) treatment group.

Where possible, data for both cohorts will be summarized in the same output.

Continuous (quantitative) variable summaries will include the number of subjects (n) with non-missing values, mean, standard deviation (SD), median, minimum, and maximum.

Categorical (qualitative) variable summaries will include the frequency and percentage of subjects who are in the particular category or each possible value. In general, the denominator for the percentage calculation will be based upon the total number of subjects in the study population for the treatment groups within cohort, unless otherwise specified.

The minimum and maximum will be reported with the same degree of precision (ie, the same number of decimal places) as the observed data. Measures of location (mean and median) will be reported to 1 degree of precision more than the observed data and measures of spread (SD) will be reported to 2 degrees of precision more than the observed data.

Percentages will be presented to 1 decimal place, unless otherwise specified.

Unless otherwise indicated, all statistical tests will be conducted at the 0.05 significance level using 2-tailed tests, and *p* values will be reported. Corresponding 95% confidence intervals (CIs) will be presented for statistical tests.

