14.3.6 Other Safety Data Summary Tables		
Table 14.3.6.1.1	Safety	Summary of Quantitative Dermal Response Reaction by Study Visit, Treatment, and Cohort
Table 14.3.6.1.2	Safety	Summary of Qualitative Dermal Response Reaction by Study Visit, Treatment, and Cohort
Table 14.3.6.1.3	Safety	Summary of Application Site Reaction Other Effects by Study Visit, Treatment, and Cohort
Table 14.3.6.2.1	Safety	Summary of Vital Signs by Study Visit, Treatment, and Cohort
Table 14.3.6.2.2	Safety	Shift from Baseline in Weight by Study Visit, Treatment, and Cohort
Table 14.3.6.3	Safety	Summary of 12-Lead Electrocardiogram Interpretation by Study Visit, Treatment, and Cohort
Table 14.3.6.4.1	Safety	Summary of Quick Inventory of Depressive Symptomatology-Self-Report (QIDS-SR) Total Score by Study Visit, Treatment, and Cohort
Table 14.3.6.4.2	Safety	Summary of Quick Inventory of Depressive Symptomatology-Self-Report (QIDS-SR) Total Score Severity Levels by Study Visit, Treatment, and Cohort
Table 14.3.6.4.3	Safety	Shift from Baseline in Quick Inventory of Depressive Symptomatology-Self-Report (QIDS-SR) Total Score Severity Levels by Study Visit, Treatment, and Cohort
Table 14.3.6.5	Safety	Summary of Concomitant Medications by ATC Class Level 4, PT, Treatment, and Cohort

AD-ST-33.04 Effective date: 30-Jun-2017

Statistical Analysis Plan,
Sponsor Arcutis, Inc.
Protocol Number ARQ-151-101
PCN Number ARCU7063

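### Dermal Response scores are summarised only visit by visit, so no planned table shows each subject's worst score, the shift from Visit 2, or how many subjects ever reached the protocol's threshold of 5

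*SAP*

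**What the plan says.** In Cohort 2 the 0-7 Dermal Response score is taken at Baseline (Visit 2) and at Visits 3 to 6 (protocol 8.12.6). Protocol 8.11.2 attaches an action to it. For an irritation-type reaction "with a severity of a Dermal Response Score of 5 (erythema, edema and papules) or greater", treatment pauses for up to a week and may resume once the reaction has settled. If the reaction returns, treatment stops for good.

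Protocol 9.3 plans counts only: "The numeric application site reaction scores will be summarized individually by using number and percentage of subjects by visit". SAP 9.2 keeps this ("The numeric application site reaction scores will be summarized individually by using number and percentage of subjects by visit and treatment within cohort") and then adds a second sentence. That sentence begins "The numeric application site reaction scores will be summarized by visit and treatment within cohort, in both a continuous manner (using summary statistics" and continues "and a categorical manner (using number and percentages). The character other effects scores will be summarized by visit and treatment". The table list has a quantitative table (14.3.6.1.1) and a categorical one (14.3.6.1.2, "Summary of Qualitative Dermal Response Reaction by Study Visit, Treatment, and Cohort"), both by study visit.

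SAP 6.1.5, which covers all analyses, uses an unscheduled or repeat measurement only when the scheduled one is missing. Shift tables are planned for laboratory values (SAP 9.3), weight (SAP 9.4) and QIDS-SR category (SAP 9.6). None is listed for Dermal Response.

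**The concern.** Safety against vehicle is part of the primary objective for Cohort 2 (protocol 8.3.1), and for a first-in-human topical product local tolerability is central to it. The question a reader of the report will ask is how many subjects in each arm had a reaction serious enough to meet the protocol's own threshold. That is a count of subjects over the whole treatment period. Protocol 8.11.2.1 points the same way: among the factors bearing on unblinding it lists the number of subjects involved. The planned tables give a separate count at each visit, and those counts cannot be added up to the number of subjects affected.

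Two features sharpen the gap. First, a reaction that reaches 5 between visits, leads to a pause and settles before the next scheduled visit leaves no trace in a score table. Second, the scale grades erythema, edema and papules on plaques that are already inflamed, so a later score is hard to read without the same subject's Visit 2 score beside it. That score is collected, but no planned text or title uses it as the reference for change.

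**Working it through.** The documents give no expected reaction rate, so there is no plan figure to reproduce. The rates below are assumed for illustration. The arm size is from the documents: 84 subjects randomised 1:1:1 (protocol synopsis; SAP 3.2 and 3.5), so 84 / 3 = 28 per arm. There are four post-baseline assessments (Visits 3, 4, 5 and 6).

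**1. Can the proportion ever affected be recovered from by-visit counts?** Suppose 1 of 28 subjects scores 5 or more at each of the four visits.
- Each by-visit entry is 1/28 = 3.6%.
- If it is the same subject each time, the proportion ever affected is 1/28 = 3.6%.
- If it is four different subjects, it is 4/28 = 14.3%.

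The same four table entries fit both cases. The range is a factor of 1 to 4, and nothing in the table says where in it the truth lies.

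**2. What do the summary statistics add?** Take the four-different-subjects case, each scoring 5 once and everyone else 0. The mean at each visit is 5 x 1 / 28 = 0.18, against 14.3% ever at the threshold. The steps are ordinal descriptors, so 0.18 has no direct clinical reading.

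**3. What would a shift from Visit 2 add?** Suppose all 28 score 1 at Visit 2. Later, 4 rise to 3, m fall to 0 and the rest stay at 1. The later mean is (4 x 3 + (24 - m) x 1) / 28:

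| m | Later mean (Visit 2 mean 1.00) | Subjects worsened |
|---|---|---|
| 4 | 32/28 = 1.14 | 4/28 = 14.3% |
| 8 | 28/28 = 1.00 | 4/28 = 14.3% |
| 16 | 20/28 = 0.71 | 4/28 = 14.3% |
| 24 | 12/28 = 0.43 | 4/28 = 14.3% |

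The mean can fall by more than half while the number worsened is fixed. In this example the categorical table would still show four subjects at 3. It hides worsening only when other subjects vacate the same category: if four go from 1 to 3 while four others go from 3 to 1, the by-visit counts do not change at all. A shift table shows both movements.

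**4. Which scores never reach a table?** A score of 5 recorded at an unscheduled visit inside the Visit 3 window (Days 2 to 8, SAP Table 4) is set aside under SAP 6.1.5 if the scheduled Visit 3 score exists. It then appears only in Listing 16.2.9.1.

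**5. Do the adverse event outputs supply the count?** In part. Permanent stops recorded as adverse events are tabulated (Table 14.3.1.5) and listed. Table 14.3.1.3 shows events by maximum severity, but on the 5-grade adverse event scale (SAP 9.1), not the Dermal Response scale, so it cannot identify who reached 5. Temporary interruptions have no table. Missed doses are listed (16.2.5.3) and doses received are summarised (SAP 7.4), neither by reason.

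**The case against.** The strongest reply is that little is lost. Every scheduled score of 5 or more appears as a count in Table 14.3.6.1.2 at the visit where it occurred, and a 0 at the next visit does not erase it. The summary statistics include the maximum (SAP 4.1), so the worst scheduled score in each arm at each visit is shown. All scores are listed by subject. This is a descriptive Phase 1/2a safety summary of about 28 subjects per arm, and a worst-score table could be built afterwards. All of that stands, and it limits the point to what is not combined across visits and what is unscheduled.

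Several stronger readings are tempting, and the documents do not support them.
- *Scores are reported only as means.* They are not: SAP 9.2 plans counts and percentages in two sentences, and they have their own table.
- *Treatment-stopping reactions disappear.* Permanent stops recorded as adverse events have a table and a listing. Only temporary pauses lack one.
- *Whether a threshold reaction becomes an adverse event is left to discretion.* The sentence in protocol 8.12.6, "Changes in Dermal Response scores, consistent with disease fluctuation, will only be recorded as an AE if the Investigator considers the change to be worse", concerns changes that look like disease fluctuation. An irritation reaction scoring 5 or more fits the general definition in protocol 8.16.1.1.
- *Absent subjects dilute the percentages.* SAP 4.1 says "the denominator for the percentage calculation will be based upon the total number of subjects in the study population for the treatment groups within cohort", but as a general rule that allows exceptions. The table shells, which would show the denominator used, are not in the public copy.
- *Clearing psoriasis will make the active arms look better tolerated.* This is plausible because the scale grades erythema. But sites are told to separate reactions from existing psoriatic inflammation, and no figure in the documents sizes the effect.

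**Conclusion.** The point holds as a gap in the safety summaries. From the SAP text and table titles, Dermal Response is summarised only by visit. No worst post-baseline score, shift from Visit 2, count of subjects ever at 5 or more, or table of temporary interruptions is planned. A score of 5 or more from an unscheduled visit can be absent from every score table.

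On size, 1/28 at each of four visits fits an ever-affected proportion from 3.6% to 14.3%. A reader might infer a fourfold understatement, but that is the extreme, reached only if each affected subject reacts at one visit and all are different subjects. That the proportion cannot be recovered from the tables does not depend on the assumed rate; the percentages do. Masking of individual worsening by falling scores is possible but not quantified.

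One limit remains. With the shells removed, a change-from-baseline column inside Table 14.3.6.1.1 cannot be ruled out, though it would not give an ever-affected count. No efficacy conclusion is affected.

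**What to change.** For Cohort 2, add to SAP 9.2 and to the table list, by treatment received:
- each subject's worst post-baseline Dermal Response score, with the number and percentage ever scoring 5 or more;
- a shift table from the Visit 2 score to the worst post-baseline score.

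Amend SAP 6.1.5 to say that unscheduled assessments count for these two summaries. Otherwise the new text in 9.2 would contradict the rule for all analyses. Confirm that the Visit 2 score is taken before the first application, as the SAP 6.1.1 definition of baseline requires; the documents do not say so for this assessment. Keep the by-visit count table. The mean and SD table may stay as a supplement. Cohort 1, with scores on Days 1 and 2 only, can stay as planned.

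The cost is SAP wording and one or two descriptive tables, with no new data collection. The reported reaction rate may look less favourable than the by-visit percentages.

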9.3. Clinical Laboratory Evaluations

All summaries of laboratory values will be presented using SI units. All hematology, chemistry, urinalysis, and other results will be listed by subject and timing of collection. Abnormal results will be flagged in the listings.

Observed values and change from baseline at each time point for continuous hematology, chemistry, and urinalysis results will be summarized using descriptive statistics by visit and treatment within cohort. Categorical urinalysis results will be summarized using frequencies by visit and treatment within cohort. Shifts from baseline for clinical laboratory values below, within, or above the normal range will be provided for hematology, chemistry, and urinalysis results.

Pregnancy test results and hormonal laboratory results will be listed.

